9.4.2 Pharmacodynamic Statistical Methodology

Not applicable.

9.5 Pharmacokinetic/Pharmacodynamic Assessment

Exploratory graphical PK/PD analyses may be conducted to evaluate the relationship between LY3337641 concentrations (or exposure) and PD measures. Additional model-based analyses may be conducted if deemed appropriate. Any PK/PD analyses will be the responsibility of Eli Lilly and Company.

9.6 Safety and Tolerability Assessments

9.6.1 Adverse events

Where changes in severity are recorded in the Case Report Form (CRF), each separate severity of the adverse event (AE) will be reported in the listings, only the most severe will be used in the summary tables. A pre-existing condition is defined as an AE that starts before the subject has

provided written informed consent and is ongoing at consent. A non-treatment emergent AE is defined as an AE which starts after informed consent but prior to dosing. A treatment-emergent AE is defined as an AE which occurs postdose or which is present prior to dosing and becomes more severe postdose. AEs by day of onset will be presented for Cohorts 1 and 5.

All AEs will be listed. Treatment-emergent AEs will be summarized by population, treatment, severity and relationship to the study drug. The frequency (the number of AEs, the number of subjects experiencing an AE and the percentage of subjects experiencing an AE) of treatment-emergent AEs will be summarized by population, treatment, Medical Dictionary for Regulatory Activities (MedDRA) version 19.1 system organ class and preferred term. The summary and frequency AE tables will be presented for all causalities and those considered related to the study drug. Any serious AEs will be tabulated.

9.6.2 Concomitant medication

Concomitant medication will be coded using the World Health Organization (WHO) drug dictionary (Version September 2016). Concomitant medication will be listed.

9.6.3 Clinical laboratory parameters

All clinical chemistry and hematology data will be summarized by population, treatment and timepoint, and listed. Urinalysis data will be listed. Additionally clinical chemistry, hematology and urinalysis data outside the reference ranges will be listed.

Values for any clinical chemistry, hematology and urinalysis values outside the reference ranges will be flagged on the individual subject data listings.

9.6.4 Vital signs

Vital signs data will be summarized by population and treatment together with changes from baseline, where baseline is defined as Day 1 predose. Figures of mean vital signs and mean changes from baseline profiles will be presented by population and treatment. Furthermore, values for individual subjects will be listed.

9.6.5 Electrocardiogram (ECG)

The ECG data will be obtained directly from the 12-lead ECG traces. These data include the PR, QT, QRS duration and heart rate. In addition, QTcF (the QT interval corrected using Fridericia's formula) will be calculated as follows:

$$QTcF = \frac{QT}{\sqrt[3]{(60/HR)}}$$

The ECGs will be collected in triplicate; the mean of triplicates will be used in the analysis. The ECG data will be summarized by population and treatment together with changes from baseline, where baseline is defined as the mean of the Day 1 predose measurements. Figures of mean ECG data and mean changes from baseline will be presented by population and treatment. As

suggested by ICH E14 Guideline, the frequency of subjects with a maximum increase from baseline in QTcF interval will be summarized for each population and treatment according to the following categories: >30 ms and >60 ms. In addition, the frequency of subjects with QTcF postdose values, according to the following categories: >450 ms, >480 ms and >500 ms, will be summarized by population and treatment.

9.6.6 Other assessments

All other safety assessments not detailed in this section will be listed but not summarized or statistically analyzed.

9.6.7 Safety and Tolerability Statistical Methodology

The relationship between concentrations of LY3337641 and changes from baseline QTcF (Δ QTcF) will be explored to assess the effect of LY3337641 concentration on the Δ QTcF. A scatter plot of the change from baseline in QTcF versus the concentrations with the fitted lines will also be plotted. A linear mixed-effects model will be fitted with the Δ QTcF as the response, the time-matched concentration as a covariate, population (Japanese/Caucasian) as a fixed effect, the population-by-concentration interaction term, and subject as a random effect. If there is no evidence of a difference between Japanese and Caucasian subjects, population will be removed from the model. The intercept and slope from the model along with their 90% CI will be reported. In addition, prediction intervals using C_{\max} estimated at the highest given dose in the study will be reported together with its 90% prediction intervals.

Example SAS code:

```
proc mixed data=ecg alpha=0.1;  
  class subject race;  
  model change = conc race race*conc / cl solution ddfm=kr;  
  random subject;  
run;
```

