10.3. Statistical Analyses

Statistical analysis of this study will be the responsibility of Eli Lilly and Company or its designee.

PK analyses will be conducted for all subjects who receive at least 1 dose of LY3337641 and have evaluable PK data. PD analyses will be conducted on the full analysis set, which includes all data from all subjects receiving at least 1 dose of LY3337641 or placebo. Safety analyses will be conducted for all randomized subjects who receive at least 1 dose of LY3337641 or placebo and have at least 1 postdose safety assessment, regardless of whether they have completed all protocol requirements. For QT interval, all subjects with at least 1 postdose QT interval measurement will be included in the analysis.

Summary statistics, data tabulations, and data graphs will be provided and may be separated by race (Japanese and Caucasian) as appropriate.

Additional exploratory analyses of the data will be conducted as deemed appropriate. Study results may be pooled with the results of other studies for population PK/PD analysis purposes.

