4.3 Exploratory Objectives

- To explore the PD following single and multiple doses of LY3337641 in healthy Japanese and Caucasian subjects.

- To explore the safety, tolerability, PK, and PD of LY3337641 in Japanese subjects in relation to Caucasian subjects.
- To explore the effect of LY3337641 on ECG findings in healthy Japanese and Caucasian subjects.

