7. SAMPLE SIZE JUSTIFICATION

Up to 60 subjects may be enrolled so that approximately 36 to 48 subjects complete the study. The sample size is customary for Phase 1 studies evaluating safety, PK, and/or PD parameters and is not based on the power of statistical hypothesis tests. Subjects who are randomized but discontinue the study may be replaced in the same cohort and race (Japanese or Caucasian) at the discretion of the sponsor.

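### The concentration–QTcF model in SAP 9.6.7 promises no confidence interval for the mean ΔQTcF at the highest-dose Cmax, and drops population on absence of evidence in a study not sized to find a difference

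*SAP*

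**What the plan says.** Protocol 10.3.1.2 asks for an exploration of LY3337641 concentration against change from baseline in QTcF and leaves the QT detail to the SAP.

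SAP 9.6.7 fits a linear mixed model to ΔQTcF with time-matched concentration, "population (Japanese/Caucasian) as a fixed effect, the population-by-concentration interaction term, and subject as a random effect". On reporting:

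- **Coefficients:** "The intercept and slope from the model along with their 90% CI will be reported".
- **Population:** "If there is no evidence of a difference between Japanese and Caucasian subjects, population will be removed from the model".
- **At Cmax:** prediction intervals at the Cmax "estimated at the highest given dose in the study will be reported together with its 90% prediction intervals". The sentence names prediction intervals twice, so the first mention may be a slip for predicted values. The only interval named is still a prediction interval.
- **Example code:** PROC MIXED with `alpha=0.1`, `cl` and `solution`, and no ESTIMATE statement.

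Elsewhere in the SAP, section 9.6.5 has ECG summaries and changes from baseline by population, and "the frequency of subjects with a maximum increase from baseline in QTcF interval will be summarized for each population and treatment". Section 7 says the sample size "is not based on the power of statistical hypothesis tests". Section 4.3 lists among the exploratory objectives "To explore the effect of LY3337641 on ECG findings in healthy Japanese and Caucasian subjects", and separately the comparison of Japanese with Caucasian subjects.

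**The concern.** **Interval.** The stated aim is the effect of concentration on ΔQTcF, which is a question about a mean. A prediction interval answers a different question, namely where an individual value may fall. Most of its width is between- and within-subject scatter, which more subjects would not remove. Separate CIs for intercept and slope cannot be combined into a CI for the predicted mean without their covariance, which the SAP does not say it will report.

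**Removal rule.** Finding no evidence of a difference in a small study does not show that there is none. The SAP does not say which population term is judged, by what test or at what level, or whether the interaction goes too. Once population is out, a single pooled slope may be read as holding for both populations. The reader need not be shown how large a difference the data leave open, although comparing the populations is a stated objective.

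**Working it through.** The plan gives no QTc precision or power figure to reproduce. The sizes below are illustrations.

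**Inputs from the documents**
- Active subjects without optional Cohort 5: Japanese 6 + 3 + 3 + 3 = 15; Caucasian 3 + 3 + 3 + 3 = 12; total 27. Placebo: 5 + 4 = 9. All: 27 + 9 = 36, the lower figure for completers.
- At 160 mg: 3 Japanese and 3 Caucasian active subjects.
- Matched post-first-dose ECG/PK times in the Schedule of Activities: 10 in single-dose and 22 in multiple-dose cohorts.

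**Assumptions (not in the documents)**
- *Set A:* ΔQTcF SD 4–5 ms between and 6–8 ms within subjects; one-compartment oral PK, dose-proportional, half-life 2–8 h, exposure CV 30–50%.
- *Set B:* SD pairs 4/6, 6/8 and 8/10 ms; half-life 3 or 12 h; no exposure variability; end-of-study time omitted.

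**Formulas.** With intercept a, slope b and c = the 160-mg Cmax:
- Effect relative to zero concentration: b·c, SE = c·SE(b).
- Predicted mean change: a + b·c, variance = Var(a) + c²Var(b) + 2c·Cov(a,b).
- Prediction variance: the variance of a + b·c, plus the between-subject variance (new subject's mean), plus the within-subject variance as well (new observation).
- Probability that a level-α interaction test removes population when the true slope difference at c is d: Φ(z − d/SE) − Φ(−z − d/SE), with z the 1 − α/2 normal quantile.

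**One case with numbers in** (set B, 27 active, SD 4/6, half-life 3 h, population removed; t on 25 df = 1.708)
- Mean: SE 1.64 ms; 90% half-width 1.708 × 1.64 = 2.80 ms.
- New observation: 1.708 × √(1.64² + 4² + 6²) = 12.6 ms, about 4.5 times wider.
- New subject's mean: 1.708 × √(1.64² + 4²) = 7.4 ms.
- Full model, slope difference at c: SE 3.48 ms. For d = 5 at 0.05, d/SE = 1.44 and Φ(1.96 − 1.44) = 0.70; the second term is negligible.
- 90% half-width of that slope difference (t on 23 df = 1.714): 1.714 × 3.48 = 6.0 ms.

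**Ranges at the 160-mg Cmax** (90% half-widths in ms)

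| Quantity | Set A, 27 active | Set B, with or without placebo |
|---|---|---|
| Mean, population removed | 2.2–3.5 | 2.7–4.9 |
| Prediction, new observation | 12.5–16.5 | 12.5–22.4 |
| Prediction, new subject's mean | 7.2–9.2 | 7.3–14.5 |
| Mean, Japanese (population kept) | 3.2–4.9 | 3.8–6.9 |
| Mean, Caucasian (population kept) | 3.3–5.0 | 3.9–7.2 |
| Removed at 0.05, true 5-ms slope difference | 53–78% | 69–88% |
| Removed at 0.10, same difference | 41–67% | 57–80% |

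Under set A, a check by simulation with variances estimated by REML gave removal in 56–79% of trials at 0.05. The slope difference has a 90% half-width of about 4.5–7 ms under set A. Under set B it is wider: at the largest SE, 6.53 ms, it is 1.714 × 6.53 = 11.2 ms.

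Protocol 10.3 says "For QT interval, all subjects with at least 1 postdose QT interval measurement will be included in the analysis", which could bring placebo subjects into the model at zero concentration. That barely matters: under set A the half-width for the mean becomes 2.2–3.4 ms.

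**The case against.** The other side has four good points.

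1. *The slope CI already answers much of the first part.* A reader might infer that the SAP offers no interval for the effect at Cmax. That goes too far. The effect relative to zero concentration is b·c, and its CI is the promised slope CI times Cmax. Its half-width is 2.3–3.5 ms under set A, almost the same as for the predicted mean. What is missing is the CI for a + b·c. That quantity includes change unrelated to drug, because the model has no time or treatment term.

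2. *The code already computes the interaction's CI.* With `alpha=0.1` and `cl solution`, fitting the full model prints the slope difference with a 90% CI. This stands. The remaining gap is that the SAP does not require the CI to be reported after removal.

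3. *The rule need not be read in its worst form.* A reader might suppose that only the population main effect is tested. That term is the difference at zero concentration, so the test would remove population about 95% of the time at 0.05 whatever the slope difference. The text does not support resting the case there: it speaks of a difference between the populations generally, and removing population most naturally takes the interaction with it. The interaction-test figures are the ones to use.

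4. *Nothing is decided on this model.* A reader might infer that pooling hides the population comparison altogether. It does not: SAP 9.6.5 reports ECG means, changes and threshold counts by population in any case. These do not, however, give a CI for the slope difference.

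The prediction interval is also not redundant. It gives a model-based range at one concentration, whereas the counts cover any postdose time.

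**Conclusion.** The point holds in a limited form. SAP 9.6.7 names no CI for the predicted mean ΔQTcF at the highest-dose Cmax. It also uses absence of evidence to drop population, in a study not sized for that check. Under the assumed variability and PK shape, an interaction test at 0.05 would miss a 5-ms slope difference in roughly 55–80% of trials, and in up to about 88% with larger SDs. The removal criterion can therefore be met often when a difference of that size exists, and the estimated difference need not then be reported.

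The millisecond values and percentages rest on assumptions, and the two sets differ enough that neither should be quoted as the trial's precision. The direction is the same in both. Severity is low: the analysis is exploratory, the documents set no QTc decision threshold, and the summaries by population remain.

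**What to change.** Two changes to SAP 9.6.7:

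(a) Replace the last sentence with: *The model-predicted mean ΔQTcF with two-sided 90% CI will be reported at the geometric mean Cmax of the highest dose given, overall and by population. Any prediction interval is supplementary and labelled as describing individual values.*

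(b) Replace the removal rule with: *Both the model with population and interaction (population-specific slopes and the slope difference, with 90% CI) and the model without population terms will be reported, whatever the result.*

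In the code, add ESTIMATE statements for the predicted means and the population-specific slopes. SAP 9.3.2 already uses such statements, with confidence limits, for the power model. The slope difference is already in the full-model output and need only be carried into the report.

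**Cost:** two sentences and a few lines of code, with no new data. Two models are shown instead of one. The CIs by population at Cmax are wider than the pooled one (about 3–5 against 2–3.5 ms under set A), and the slope difference will have a wide CI, about ±4.5 to ±7 ms under the same assumptions. That width shows the reader how little the study can say about a difference.

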10. INTERIM ANALYSES

The Lilly study team is unblinded. Data may be analyzed while the trial is ongoing, but no changes to the study design are planned. An assessment committee will not be formed.

Up to 3 interim analyses are planned to occur during the study according to the following timeframe: when at least safety and PK data of (1) Day 2 predose (24 hours after first dose) become available from at least 11 subjects in Cohort 1, including at least 4 Caucasian subjects; (2) Day 17 (48 hours after last dose) become available from Cohort 1; and (3) Day 29 become available from Cohort 1. All safety and PK data available from other cohorts by this time will be included in the interim analysis. The purpose of the interim analysis is to support the inclusion of Japanese subjects in future studies. The investigator and the Lilly clinical pharmacologist will review the safety and tolerability data, and the PK/PD scientist will review the PK data. The investigator will remain blinded, and the Lilly study team will be unblinded during this interim review.

Information that may unblind the study during the analyses will not be reported to study site or blinded personnel until the study has been unblinded.

Additional interim analysis may be conducted at any time throughout the study as required to ensure subject safety or to help guide dosing.

If an unplanned interim analysis is deemed necessary, the Lilly clinical pharmacologist, clinical research physician/investigator, or designee will consult with the appropriate medical director or designee to determine if it is necessary to amend the protocol.

11. CHANGES FROM THE PROTOCOL SPECIFIED STATISTICAL ANALYSES

There were no changes from the protocol specified statistical analyses.

13. DATA PRESENTATION

13.1 Derived Parameters

Individual derived parameters (e.g. PK parameters) and appropriate summary statistics will be reported to three significant figures. Observed concentration data, e.g. C_{max} , should be reported as received. Observed time data, e.g. time of maximum observed drug concentration (t_{max}), should be reported as received. N and percentage values should be reported as whole numbers. Median values should be treated as an observed parameter and reported to the same number of decimal places as minimum and maximum values.

13.2 Missing Data

Missing data will not be displayed in listings.

13.3 Insufficient Data for Presentation

Some of the TFLs may not have sufficient numbers of subjects or data for presentation. If this occurs, the blank TFL shell will be presented with a message printed in the centre of the table, such as, “No serious adverse events occurred for this study.”

Leo Document ID = 44d88d91-e75b-415b-bf2c-637f2e27aa4a

Approver: PPD
Approval Date & Time: 23-Mar-2017 15:32:13 GMT
Signature meaning: Approved

Approver: PPD
Approval Date & Time: 23-Mar-2017 23:43:40 GMT
Signature meaning: Approved

Approver: PPD
Approval Date & Time: 24-Mar-2017 13:18:47 GMT
Signature meaning: Approved
